Study Duration	
The duration of the intervention for participants is 13 weeks: 3 weeks baseline data collection, 6 weeks intervention, post-intervention follow-up 4 weeks after intervention completion. Total participant duration from first contact with participants will be approximately 16 weeks.
 
The total expected duration of the study is 13 months. Planned start date: February 2022 (dependant on approval by ethics committee). The research will be submitted in the form of a thesis in partial fulfilment of the requirements for the Trent Doctorate in Clinical Psychology. Planned submission date: February 2023.

Objectives	
The primary research question is: When delivered in a guided self-help format, is the NHA effective in reducing parent-reported children's behavioural problems?
 
The secondary research questions are:
 
 1. When delivered in a guided self-help format, is the NHA effective in: 
 a. reducing negative parenting practices? b. increasing parental reflective functioning? 2. To what extent is the NHA a feasible and acceptable intervention for parents of children with behavioural problems when delivered in a guided self-help format?
Outcome Measures	Measures: Brief Problem Monitor (BPM; Achenbach et al., 2011), Psychological Outcomes Profiles (PSYCHLOPS; Ashworth et al., 2009), Multidimensional Assessment of Parenting Scale (MAPS; Parent & Forehand, 2017); Parental

	
Reflective Functioning Questionnaire (PRFQ; Luyten et al., 2017), Warwick-Edinburgh Mental Well-Being Scale (WEMWBS; Tennant et al., 2007)
 
A semi-structured change interview (based on Rodgers and Elliott (2015) will be completed with participants 4 weeks post-intervention.

Data Analysis	
Visual analysis and calculations of reliable and clinically significant change will be used to analyse the quantitative data. Framework analysis as outlined by Gale et al. (2013) will be used to analyse the change interviews.

KEY WORDS

Nurtured Heart Approach; parenting; child behavioural problems; single case design.

Table of Contents

SIGNATURE PAGE.....	3
STUDY/TRIAL CONTACTS.....	4
FUNDER DETAILS.....	4
STUDY SUMMARY	5
KEY WORDS	6
LIST OF ABBREVIATIONS	9
STUDY MANAGEMENT.....	10
ROLE OF STUDY SPONSOR AND FUNDER.....	10
STUDY BACKGROUND and RATIONALE	10
Development of the problem	10
Interventions	11
STUDY OBJECTIVES AND PURPOSE	12
PURPOSE AND PRIMARY OBJECTIVES.....	12

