Behavioural problems are common in childhood; estimates suggest that between 5% and 14% of children exhibit behavioural difficulties (Green et al., 2005; Merikangas et al., 2009). In the UK, 30% of general practitioner (GP) child consultations and the majority of referrals to children's mental health services are for behavioural problems (National Institute for Health and Care Excellence (NICE), 2017). It is clear, therefore, the scale of the problem is significant.

The term "behavioural problems" is widely used but its precise meaning is often not clear. However, defining what is meant by behavioural problems is difficult for several reasons. Problematic behaviour is age and context dependent; tantrums are developmentally appropriate at the age of two but not past the age of four (Gardner & Shaw, 2008). There is also a subjective judgement as to what behaviour presents a problem, and for whom.

Achenbach (1966) identified two broad dimensions of behaviour in children: externalising and internalising behaviours. Externalising behaviours are generally defined as aggression, cruelty and rule-breaking behaviours (Achenbach, 1978; Achenbach & Edelbrock, 1979; Frick et al., 1993). Unlike internalising behaviours such as anxiety, which are most problematic for the child themselves, externalising behaviours mainly present problems for others (Carr, 2016). The focus of this study will be on externalising behaviour in childhood.

Behavioural problems in childhood have numerous negative correlates in adolescence and adulthood. Children demonstrating higher levels of externalising behaviour have increased risks of poor school attendance, poor educational attainment, anxiety and mood disorders, substance misuse, unemployment, and criminal offending (Colman et al., 2009; Kratzer & Hodgins, 1997). Consequently, childhood behavioural problems have a pervasive impact on both individual and societal levels.

Development of the problem

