The Parental Reflective Functioning Questionnaire (PRFQ) will be used to assess parental reflective functioning. The PRFQ has not been validated by developers for parents of children aged six to eleven (Luyten et al., 2017). However, there is preliminary evidence that the measure is valid in children up to the age of ten (Pazzaglia et al., 2018). Consequently, the PRFQ will be used for participants of this study as, despite the limited validation in age range of the PRFQ, it is the only measure in existence that captures parental reflectivity.

Ideographic measure

An ideographic measure is included to capture parents' perception of the problems and assess any change. The Psychological Outcomes Profiles (PSYCHLOPS; Ashworth et al., 2009) items will be generated with each participant at the beginning of the baseline phase. The PSYCHLOPS is more proportionate than the Personal Questionnaire (Elliott et al., 2016) as it focuses on two problem areas rather than ten; this will reduce the time burden on participants during the generation of items and completion of the measure.

General wellbeing measure

Understanding general wellbeing is important as it is likely to impact parenting behaviour. The Short Warwick-Edinburgh Mental Well-Being Scale (SWEMWBS; Tennant et al., 2007) will be used instead of the General Health Questionnaire (GHQ-12; McCabe et al., 1996) because the GHQ-12 primarily screens for psychopathology whereas the SWEMWBS also captures positive aspects of wellbeing.

Change interview

One month post intervention the participants will also be asked to take part in a semi-structured change interview (Rodgers & Elliott, 2015). The purpose of the interview is to capture parents' views of any changes resulting from their participation in the NHA intervention. The addition of this qualitative data will allow for a more comprehensive evaluation of the intervention.

STUDY DESIGN

The study proposes using a non-concurrent across-participant multiple baseline A-B single case design. The baseline period (A) precedes the intervention period (B), where the NHA is delivered in a guided self-help format over six weeks. Data will be collected using psychometric measures and post-intervention data

collection will also include a qualitative semi-structured change interview. Full details are given below in "Study Procedure".

DATA ANALYSIS

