Visual analysis is the suggested method of analysing single case design data (Barlow et al., 2009) and consequently will be used to analyse the data resulting from this research. The data will be visually represented on graphs and examined for trends in the data indicating if and when change has occurred across the process measures for the three variables of interest. The data will also be analysed to establish if any changes are reliable and clinically significant. Assessment of reliable change identifies if change is genuine or resulting from measurement error; this will be calculated using the Reliable Change Index (Jacobson & Truax, 1991). If changes prove reliable, they will be analysed for clinical significance (Jacobson & Truax, 1991). The change interviews will be transcribed verbatim by the doctoral student and analysed using framework analysis as outlined by Gale et al. (2013). NVivo will be used to conduct the framework analysis.

Data analysis will be completed by the doctoral student with support from the research supervisors (CI and collaborator). No interim analysis are planned.

STUDY SETTING

The study will be run across two mental health trusts in the East Midlands. The specialist children's services (Child and Adolescent Mental Health Service; CAMHS) within [redacted NHS Trust] will be the primary study site. The CAMHS service consists of four locality teams across the county, all of which work together to form one service. The population being recruited from will be parents/carers of children on the waiting lists for these services. Recruitment will be supported by staff within these services who are aware of the research project and its aims.

The secondary study site will be CAMHS services within [redacted NHS Trust]. Recruitment will only occur in the secondary study site if it has not been possible to recruit sufficient participants from the primary study site. Again, recruitment will be focused on parents/carers of children on the waiting lists for CAMHS services and will be supported by clinical psychologists within CAMHS who are aware of the research project and its aims.

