- The family is current receiving active multi-agency involvement (e.g. social care, police or youth offending in addition to NHS services).
- The parent/carer is aged under 18.
- The parent/carer is unable to read or speak English fluently.

Crnic et al. (2004) state the function of behavioural problems is often different for children with a developmental delay or learning disability, making the NHA potentially unsuitable. Similarly, multi-agency involvement and parents aged under 18 years old (legally children themselves) indicate a level of need beyond what would be appropriate for a self-help intervention. The language requirement is necessary for the participants to be able to read the self-help chapters and partake in the guided self-help conversations.

Sampling

The study aims to recruit six participants and convenience sampling will be used to identify the participants.

Size of sample

Single case designs typically have between three and six participants; consensus indicates three cases is the minimum to demonstrate an experimental effect (Kratochwill et al., 2010), while more than six participants is unlikely to be feasible given the amount of data that is required from each participant in single case design research (Barlow et al., 2009)

This study aims to recruit six participants. If successful, this maximises the power of the design without compromising feasibility. If recruitment proves challenging, there is capacity to reduce numbers to three participants without invalidating the findings. Participants will be replaced if drop-out occurs during the baseline phase.

Sampling technique

Convenience sampling will be used to select the participants. Staff working in the specific services will be aware of the eligibility criteria for the study and will identify potential participants. If there are more than six parents/carers willing to participate, participants will be contacted in the chronological order by which they were identified by staff.

This will not result in a representative sample. However, this is not a problem in single case research designs (Barlow et al., 2009), as the small number of participants renders the sample unrepresentative regardless of the sampling technique. The strength of the design comes instead from the systematic and repeated measurement of specific variables (Barlow et al., 2009).

RECRUITMENT

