The process for obtaining participant informed consent will be in accordance with the REC guidance, and Good Clinical Practice (GCP) and any other regulatory requirements that might be introduced. The investigator or their nominee and the participant shall both sign and date the ICF before the person can participate in the study. Participants will be able to sign the ICF electronically or can sign, scan and send back the form electronically. One copy of the ICF will be kept by the participant, one will be kept by the research team, and a third will be retained in the referred child's medical records. It will be explained to the potential participants that participation in the research study will not impact the treatment as usual that they receive from the service for which the referred child is on a waiting list. Participants will be given the contact details of the research team should they have any further questions. Should there be any subsequent amendment to the final protocol, which might affect a participant's participation in the trial, continuing consent will be obtained using an amended consent form which will be signed by the participant. Capacity will be assumed for all participants as they will be adults (over the age of 18).

[figure not shown]
STUDY PROCEDURES/REGIMEN

STUDY FLOWCHART

Below are the study flowcharts written for the participant. The first explains the process of recruitment, the second explains participation in the intervention.

Flowchart

Recruitment.

Baseline Phase

The researcher contacts the participant twice per week to collect information using questionnaires (also called measures). This phase is likely to last three weeks but may be slightly longer.

The participant decides they do not want to continue taking part in the study, informs the researcher and is withdrawn from the study.

The participant no longer meets the eligibility criteria for the study. The researcher informs them and the participant is withdrawn from the study.

The participant completes the baseline phase and continues to the intervention phase.

Intervention Phase

The participant will be sent one chapter of the workbook to read each week. The researcher contacts the participant once a week to collect information using questionnaires and discuss the chapter. This phase lasts six weeks.

The participant decides they do not want to continue taking part in the study, informs the researcher and is withdrawn from the study.

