The full study documentation and data will be restricted to staff on the research team. The anonymised quantitative dataset may be uploaded and stored on the open access University of Lincoln Repository (ePrints). All documents shall be made available at all times for review by the Chief Investigator, Sponsor's designee and inspection by relevant regulatory authorities.

DISSEMINATION POLICY

The data custodian will be the Chief Investigator on behalf of the University of Lincoln.

This research will be submitted in partial fulfilment of the requirements of the Trent Doctorate in Clinical Psychology. It is the intention to submit the research to a peer-review journal to allow for wider readership. The findings may be disseminated through relevant conferences. Participants will receive a summary of the findings, unless they have opted out on the consent form. All data disseminated will be anonymised.

The total expected duration of the study is 13 months. Planned start date: February 2022 (dependant on approval by ethics committee). Planned thesis submission date: February 2023.

Authorship eligibility guidelines and any intended use of professional writers

The doctoral student will be the primary author on all publications related to this project. The chief investigator and all co-investigators will be co-authors and authorship will be decided based on contribution at the time of publication.

REFERENCES

Achenbach, T. M. (1966). The classification of children's psychiatric symptoms: a factor-analytic study. *Psychological Monographs*, 80(7), 1–37. <https://doi.org/10.1037/h0093906>

Achenbach, T. M. (1978). The child behavior profile: I. Boys aged 6–11. *Journal of Consulting and Clinical Psychology*, 46(1), 478–488.

Achenbach, T. M., & Edelbrock, C. S. (1979). The Child Behavior Profile: II. Boys aged 12-16 and girls aged 6-11 and 12-16. *Journal of Consulting and Clinical Psychology*, 47(2), 223–233. <https://doi.org/10.1037/0022-006x.47.2.223>

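### With no prospective record of school holidays or of home and school events, a change of setting near the phase switch could be read as an NHA effect, or hide one, and the planned data could not tell

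*Combined protocol and SAP*

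**What the plan says.** The Study Design section sets the design: "The study proposes using a non-concurrent across-participant multiple baseline A-B single case design". The Study Summary gives each family's timeline as "3 weeks baseline data collection, 6 weeks intervention, post-intervention follow-up 4 weeks after intervention completion". The participant flowchart says of baseline: "This phase is likely to last three weeks but may be slightly longer". No staggered baseline lengths are assigned in advance. The Dissemination Policy places the study in the calendar: "The total expected duration of the study is 13 months. Planned start date: February 2022".

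On numbers, the Sampling section says "The study aims to recruit six participants and convenience sampling will be used to identify the participants", and Size of sample adds that "there is capacity to reduce numbers to three participants without invalidating the findings".

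The primary outcome is child behaviour as reported by the parent on the Brief Problem Monitor. The measure-frequency table and the Schedule of Procedures list what is collected: five questionnaires, demographics and one change interview. Neither lists term or holiday status, or events at home or school.

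Under Data Analysis the graphs are to be "examined for trends in the data indicating if and when change has occurred across the process measures". The Reliable Change Index and clinical significance follow. Measurement error is the only rival explanation named there.

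**The concern.** In an A-B series for one family, the case for an effect is that scores move when the intervention starts. Anything else that changes at that time competes with it. For most children aged three to eleven, moving between term and holiday changes how many hours the parent sees the child, and in what setting. A house move, a separation or a school exclusion could do the same.

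The planned analysis cannot separate these explanations. Visual inspection shows when scores moved, not why. The Reliable Change Index asks only whether a change exceeds measurement error, and a real change caused by a holiday would pass. The baseline stability review does not help either: an all-term baseline followed by an all-holiday intervention phase can look perfectly stable until the switch.

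The error can run either way. A setting change could create an apparent improvement or conceal a true one. At stake is the attribution of change in individual families and, if the sample falls to three, the replication on which the study's conclusion rests.

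**Working it through.** The plan gives no figure to reproduce here, so the check has three steps.

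**1. Contacts available.** From the measure-frequency table: 3 weeks × 2 calls = 6 in baseline, 6 × 1 = 6 in intervention, and 1 at follow-up. The total is 13. The timeline is 3 + 6 + 4 = 13 weeks, as stated.

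**2. Exposure to school holidays.** The documents give no calendar, so all of the following is assumed. Holidays run 11–22 April, 30 May–3 June, 25 July–2 September and 24–28 October 2022, and from 19 December. Start dates are the 36 Mondays from 21 February to 24 October 2022. Phase A is weeks 1–3 and phase B is weeks 4–9, so the switch falls 21 days after the start.

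*Change of holiday status at the switch.* Switch dates run from 14 March to 14 November. Four breaks lie in that window, each with one entry and one exit: 4 × 2 = 8 of 36 starts (22%). The starts entering a holiday are 21 March, 9 May, 4 July and 3 October. Those leaving one are 4 April, 16 May, 15 August and 10 October. A baseline one week longer changes which starts are affected, but the same eight boundaries remain in the window.

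*Imbalance over whole phases* (holiday share of weekdays, A against B), differing by at least 50 percentage points:

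| Start | A | B |
|---|---|---|
| 4 and 11 April | 67% | 17% |
| 13 June | 0% | 50% |
| 20 June | 0% | 67% |
| 27 June | 0% | 83% |
| 4 July | 0% | 100% |
| 11 July | 33% | 83% |
| 25 July | 100% | 50% |
| 1 August | 100% | 33% |
| 8 August | 100% | 17% |
| 15 August | 100% | 0% |
| 22 August | 67% | 0% |

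That is 12 of 36. Moving the spring and autumn breaks shifts this count by one or two; about 12 to 13 is a fair summary.

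**3. What this means across families.** Let p be the chance that a setting change falls at one family's switch, with families independent. The chance that at least r of n are affected is the sum over k ≥ r of C(n,k) p^k (1−p)^(n−k). Step 2 gives p = 8/36 = 0.22; the other values are assumed, to show the range.

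| p | ≥1 of 6 | ≥3 of 6 | ≥1 of 3 | 3 of 3 |
|---|---|---|---|---|
| 0.10 | 0.47 | 0.02 | 0.27 | 0.001 |
| 0.22 | 0.78 | 0.13 | 0.53 | 0.011 |
| 0.30 | 0.88 | 0.26 | 0.66 | 0.027 |
| 0.50 | 0.98 | 0.66 | 0.88 | 0.125 |

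For example, at p = 8/36 the chance of at least one of six is 1 − (28/36)^6 = 0.78. If only one direction of change looks like benefit, p is about 4/36 = 0.11, and at least three of six has probability about 0.02.

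So at p of about 0.2 or more, one affected family is likely among six and about an even chance among three. A whole replicated pattern produced this way is unlikely unless p is high or families start together, which would break the independence assumed here.

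**The case against.** The best defence is replication. The plan relies on at least three cases, and starts at different dates make it less likely that one holiday sits at every family's switch. This stands as partial protection. It is limited because baselines are nominally equal, no stagger is assigned and the sample may fall to three.

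Some information is also recoverable. If calls are dated, school holidays can be overlaid later. Guided sessions are audio-recorded and noted in the child's record, parents are interviewed a month after the intervention, and new multi-agency involvement leads to withdrawal. That too is fair, but none of these is specified for the purpose. The recordings and notes described are of intervention sessions, not baseline calls. The interview is framed around change due to the NHA. Home events cannot be reconstructed from dates.

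Four stronger readings are tempting, and the documents support none of them:

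- *That a setting change will be read as an effect.* The documents support only that it could be, with no specified way to tell.
- *That nearly every start date is compromised.* At a 15-point threshold, 31 to 35 of 36 starts show an imbalance between phases, depending on the calendar. But a single half-term week anywhere in phase B gives 1/6 = 16.7% and crosses that line, so the count does not measure a change at the switch.
- *That no other family is ever under observation in the same week.* Six families with nine-week A-plus-B periods would need starts spread over 5 × 9 = 45 weeks to avoid overlap, and the assumed window spans 35. Overlap still does not guarantee a family in baseline at another's switch, and three families need not overlap at all.
- *That the protocol itself concedes holiday effects.* The background remark "Problematic behaviour is age and context dependent" explains why behavioural problems are hard to define. It does not say that one child's scores shift with school holidays.

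**Conclusion.** The gap is real and moderate. Followed exactly as written, the plan cannot separate a setting change near the A-B switch from an NHA effect in an individual family. The holiday part of the exposure is about 8 of 36 start dates at the switch itself, and about 12 to 13 of 36 for a phase imbalance of at least 50 points. Both rest on assumed school calendars and evenly spread weekly starts. Children not in school or nursery are outside the holiday counts. Home and school events add to the exposure by an amount the documents do not allow one to estimate. Nor do they give the effect of holidays on Brief Problem Monitor scores, so the size and direction of any bias are unknown.

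**What to change.** At each of the 13 existing calls, in both phases and at follow-up, ask two fixed questions. Was the child at school or nursery as usual since the last call? Was there any major change at home or school? Plot each reading at its actual date, with holidays and recorded events marked.

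Add a rule to Data Analysis. Where a level change begins at a recorded holiday boundary or event (for example, both fall between the same two consecutive readings), that case is reported with the competing explanation. On its own it does not count as a demonstration of effect. Term-time readings are compared where both phases have them. This cannot be a general requirement, because a 4 July start on the assumed calendar has no term-time readings in phase B.

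The cost is two short questions per call and some annotation of graphs. No extra contacts, participants or instruments are needed. The downside is that some cases may be reported as not clearly attributable.
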